## **9. DATA HANDLING AND MONITORING**

Data arising from this study is confidential. Identifiable information can only be accessed by delegated members of the study team. Anyone in the research team who does not have a substantive contract with North Cumbria Integrated Care NHS Foundation Trust or one of the recruiting NHS Trusts will need to apply for a letter of access via the NIHR research passport scheme, should they require access to identifiable study data.

Patient identifiable data will only be used within each respective Trust and by the core research team. All identifiable data is stored on password protected NHS computer systems. Anonymised data will be shared and stored using security-enabled systems such as password-protection and encryption of e-mails and files. The requirements of the Data Protection Act and NHS Code of Confidentiality will be followed at all times. All researchers will be fully trained in NHS Confidentiality and GCP. Participants' GP practices will be informed that they are taking part in the study.

All paper data will be held in secure locked environments in the office of the Research & Development department in the Cumberland Infirmary, Carlisle and West Cumberland Hospital, Whitehaven. Data released (e.g. by publication) will contain no information that could lead to the identification of an individual participant. Upon completion of the study the site files will be archived for a period of 15 years in line with local archiving policy and procedures. Direct access to data only will be granted to authorised representatives from the sponsor / host institution, grant funder and medical device provider (Joint Operations) and the regulatory authorities to permit trial-related monitoring, audits and inspections.

This investigator-initiated trial will be monitored in terms of conduct of the study by the in-house research team, led by the Chief Investigator, who will convene on a monthly basis in person or via phone/e-mail. A formal trial steering committee will not be convened for this trial – however, when data is available for 50% of the sample an interim analysis will take place to assess if there are any points of concern to consider. The study can be audited by the in-house R&D department as part of their rolling audit programme of sponsored and hosted research studies. As part of the research grant agreement, anonymised study data will be shared with Joint Operations for review and for potential publication purposes. No identifiable data, including on potential exemplar case photos, will be contained in any of this data.

## **10. GOVERNANCE OF STUDY**

## 10.1 Approvals

This study will be conducted in compliance with the protocol approved by the Health Research Authority, National Research Ethics Service, and local Trust R&D Approval, and according to Good Clinical Practice standards including the Declaration of Helsinki (1964, Amended Oct 2013). No deviation from the protocol will be implemented without the prior review and approval of the aforementioned review bodies, except where it may be necessary to eliminate an immediate hazard to a research subject. In such case, the deviation will be reported according to policies and procedures

## 10.2 Sponsor & Indemnity

North Cumbria Integrated Care NHS Foundation Trust is the sponsor of this study and therefore NHS indemnity applies for design, conduct and management of the study. The company Joint Operations has provided a grant for this study by means of provision of the VPULSE devices worth £2,660.

Patients will not be given financial incentives for taking part in the study. Travel expenses are not offered in this study since patients are not seen in clinic more frequently than they would normally attend as part of their normal care pathway.

## 11. PUBLICATION AND DATA-SHARING POLICY

The study will be registered on ISRCTN or Clinical Trials Gov website, in line with CONSORT guidelines on good practice in clinical research.

The results of this study are planned to be disseminated through:

- Peer-reviewed manuscript in scientific journal
- Internal report to the funder of the trial, company called Joint Operations

As stated in the PIL and ICF, anonymised study data will be shared with Joint Operations as part of the research grant agreement.

A summary of the main findings can be supplied to participants on request and this will be stated in the informed consent form.

## APPENDIX 1. TOOLS AND ASSESSMENTS

[figure not shown]
This appendix contains:

- Visual Descriptor Pain scale
- Short-form McGill pain questionnaire

The KOOS score and Bandage Patient Satisfaction Questionnaire are enclosed separately to this protocol.

### Visual Descriptor Pain score

[figure not shown]
How painful has your leg, the one has been operated on, been **in the last day when resting**:

Please put a vertical line on the numbered bar above. We kindly ask you consider the affected knee when you answer this question.

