### 5.2 Participant identification and research setting

Participants will be recruited from orthopaedics clinics and all eligible patients will be invited to take part until the required numbers have been achieved. Identification will be by the orthopaedics clinical team, who are supporting the study. A screening form will be completed for potentially eligible patients to confirm that they indeed meet the trial criteria.

To summarise, the orthopaedic team will:

- Identify potentially eligible patients and ask verbal consent for them being approached about the study by a member of the R&D team
- Complete the incl/excl criteria part of the screening form (if a patient has given verbal consent to being approached by the research team then they can complete the screening form)

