### **5.4 Follow-up**

Patients are in the study for a period of 12 weeks. Thereafter, the patient will be followed up as they would be in normal clinical practice. Study visits are aligned to hospital/clinic visits where possible. Baseline data can be collected on the day of surgery (prior the actual operation), and 12 day and 12 week post-surgery data can be collected when the patient attends for standard follow-up in the orthopaedics out-patient department. The data at 24 hrs, day 3, 5, and 12 falls outside these dates. For all outcome measures, data can be collected over the phone, via e-mail or by mail (whichever is preferred by the patient – mail is by use of freepost, to avoid patients incurring any costs). The researcher can also send reminders to the participant regarding the completion of certain outcome data at the aforementioned follow-up time points.

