#### **5.5.2 Secondary outcome measures**

All the outcome measures are summarised in Table 3.

Table 3. Overview of measurements

Weeks	-12 weeks to day of surgery	0 surgery	24hrs §	3 days ##	5 days ##	12 days #	6 weeks*	12 weeks
Application device post surgery		X	x					
VDS pain scale (at rest)	X		x	X	X	X	X	
VDS pain scale (walking, if capable to stand)	X		x	X	X	X	X	
McGill pain questionnaire	X		x	X	X	X	X	
Limb range of motion	X						X	
KOOS score	X						X	X
Patient satisfaction questionnaire re device use					X	X (if not returned yet at 5 days)		

\* Allowed to be up to 2 weeks early or late

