## 6.2 Eligibility criteria

### 6.2.1 Inclusion criteria

- Patient who is listed for:
  - Knee arthroplasty (replacement) surgery, either partial or total knee replacement (unilateral).
- Clinical indication, in the opinion of the treating surgeon, that compression & cooling therapy may be of benefit to the patient
- Adult patients aged > 18 years

- Mental capacity to give written informed consent

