### 6.2.2 Exclusion criteria

- Under the age of 18 years
- Unable to fully understand the consent process and provide informed consent due to either language barriers or mental capacity
- Revision of previous knee replacement or osteotomy on the index leg.
- Limited life expectancy, i.e. undergoing palliative care
- Any condition that is associated with excessive bleeding, coagulation abnormalities or any other significant haematological condition (e.g. Factor V Leiden, haemophilia).
- Cardiovascular or vascular condition that in the opinion of the treating surgeon contraindicates the use of compression bandaging, including moderate to severe peripheral arterial disease, venous leg ulcer, high dose anti-coagulant medication
- Any skin or other condition that contraindicates the use of compression and cooling therapy.
- Patients who are participating in another interventional research study involving an investigational product related to the knee procedure and its aftercare.
- The patient has concurrent (medical) conditions that in the opinion of the investigator may compromise patient safety or study objectives.
- Patient has practical or mobility issues which will prevent them from removing the device themselves

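### The pain forms scheduled before surgery ask about the leg already operated on, which misdirects baseline answers from eligible patients whose other knee has had surgery

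*Protocol*

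**What the plan says.** **Schedule.** Table 3 in section 5.5.2 marks VDS at rest, VDS walking and McGill in the pre-operative column, whose window runs from minus "12 weeks to day of surgery". The secondary objectives in the Research Protocol Summary also list these measures before surgery. Section 5.4 confirms the order: "Baseline data can be collected on the day of surgery (prior the actual operation".

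**Forms.** Appendix 1 contains the two VDS forms and the McGill form, one version of each. Each begins "How painful has your leg, the one has been operated on, been". Both VDS forms then add "We kindly ask you consider the affected knee when you answer this question". The McGill form as printed has no such line. Appendix 1 says that only the KOOS and the satisfaction questionnaire are supplied separately, so it points to no other pain form for use before surgery.

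**Eligibility.** Section 6.2.1 admits "Knee arthroplasty (replacement) surgery, either partial or total knee replacement (unilateral". The exclusion for earlier knee surgery in section 6.2.2 is "Revision of previous knee replacement or osteotomy on the index leg".

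**Mode of completion.** Section 5.4 states: "For all outcome measures, data can be collected over the phone, via e-mail or by mail".

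**The concern.** A pain score is usable only if the patient knows which knee to rate. Before surgery the stem of all three forms describes an event that has not happened to the index knee. Most patients will see what is meant. A patient with an earlier operation on the other knee has a leg that fits the description exactly, and it is not the one under study.

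At stake are the baseline VDS and McGill scores, which describe the two groups before treatment and would be the reference for any change from baseline. McGill also carries the secondary objective on type of pain (section 4.2). A score given for the wrong knee cannot be recognised or repaired afterwards, because the forms do not record which knee the patient had in mind.

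**Working it through.** The point is one of wording, so the check sets the passages side by side.

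**1. Is the form used before the event that it describes?** Yes. Table 3, the Summary and section 5.4 place all three measures before the operation, and the stem in Appendix 1 is in the past tense. No pre-operative variant is supplied or mentioned.

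**2. Can an eligible patient have an operated other knee?** Yes. The section 6.2.2 criterion names revision of an earlier replacement and osteotomy on the index leg. An earlier primary replacement of the opposite knee is neither of these, and section 6.2.1 requires only that the present procedure be unilateral. No other criterion names surgery on the other knee.

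**3. What does each form tell such a patient at baseline?**

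| Form | Leg named by the stem, read literally | Further line | Net instruction |
|---|---|---|---|
| VDS at rest | The other leg | Affected knee, most naturally the one awaiting surgery | Two cues in conflict |
| VDS walking | The other leg | Same line | Two cues in conflict |
| Short-form McGill | The other leg | None shown | Wrong leg |

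For a patient with no earlier knee surgery the stem has no literal referent, but the meaning is obvious and little data error is to be expected.

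**4. Will someone be there to clarify?** Sometimes. Baseline may be taken on the day of surgery or by phone, but section 5.4 also allows e-mail and mail.

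**5. Where do baseline pain scores enter the analysis?** Section 8.2 plans average differences between time points and names 24 hours, days 2, 3, 5 and 12, and 6 weeks. It does not name baseline, so whether change from baseline is intended is left open. The groups are compared by Mann-Whitney test. The covariates listed in section 8.3 do not include baseline pain.

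**6. Does any stated figure depend on this?** No. Table 4 rests on post-operative means of 5.0 and 3.5 with SD 2, so the effect size is (5.0 − 3.5)/2 = 0.75. A two-sided t-test at 5% with 80% power needs 28.9 per arm. Dividing by the Mann-Whitney relative efficiency 3/π gives 28.9 × π/3 = 30.26, rounded up to 31 per arm, or 62 in total, as stated. Then 62/0.7 = 88.6, against the stated 88. Baseline pain is not an input.

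**7. How many patients are exposed?** If p is the share with earlier surgery on the other knee, 88 × p are exposed, and the number who actually answer for the wrong knee is at most that. The protocol gives no p, so no count follows from it.

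**The case against.** The strongest reply is that this is an awkward tense with little consequence. A patient listed for knee replacement will normally take the affected knee to be the one awaiting surgery, so on the VDS forms the second line largely rescues the first. Staff can often clarify in person or by phone. The one form without that line, McGill, is a secondary measure. Random allocation should spread any baseline error similarly over both arms.

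Much of this stands, and it limits the point to baseline data. It does not remove it: the VDS cues still conflict for the patients concerned, McGill has no corrective line, and remote completion is allowed.

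Four stronger readings might be inferred, and the protocol does not support them.

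- *The primary outcome is corrupted.* It is a post-operative VDS score at rest. Two days after unilateral surgery, with the study device having been applied to the index knee (sections 3.1.1 and 3.1.2), confusion about which leg is meant is implausible. The between-arm comparison needs no baseline value. Section 6.1 names day 5 instead of day 2, but the argument is much the same for either day.
- *Covariate adjustment is weakened.* No adjustment for baseline pain is planned in sections 8.2 or 8.3.
- *A definite number of patients is affected.* Without a stated rate, any count would be a ceiling resting on an assumption.
- *Patients could be randomised twice, once for each knee.* Section 5.2 says that "all eligible patients will be invited to take part until the required numbers have been achieved", and no criterion expressly bars a return. But the protocol counts patients, not knees, and nothing suggests that repeat entry is intended. That is a separate eligibility question and does not follow from the wording of the forms.

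**Conclusion.** The point holds for baseline. All three pain forms are scheduled before surgery but worded for use after it. For eligible patients with earlier surgery on the other knee, the McGill stem literally asks about the wrong leg and the VDS forms give conflicting directions.

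The effect is extra error in baseline pain scores and in any change from baseline, if that is analysed. It is confined mainly to a subgroup whose size the protocol does not give. No systematic difference between arms is expected, and neither the sample size nor the primary between-arm comparison is materially affected. The conclusion assumes that the forms in Appendix 1 are the ones handed out at baseline; no others are mentioned. It is worth correcting because the remedy is nearly free and the scores cannot be repaired later.

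**What to change.** Prepare two versions of each of the three forms.

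- **Pre-operative:** 'your LEFT / RIGHT knee, the one that is going to be operated on'.
- **Post-operative:** 'your LEFT / RIGHT knee, the one operated on for this study'.

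Staff mark the side before the form is handed over, posted or e-mailed, and read it out for completion by phone. The operated side is already to be recorded under section 8.1. Add to the McGill form an index-knee line like the one on the VDS forms.

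The cost is the rewording of three one-page forms under a minor amendment. Visits, eligibility, sample size and analysis do not change.

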### Visual Descriptor Pain score

How painful has your leg, the one has been operated on, been **in the last day when walking**:

Please put a vertical line on the numbered bar above. We kindly ask you consider the affected knee when you answer this question.

## Short-form McGill pain questionnaire

How painful has your leg, the one has been operated on, been **generally in the last day**

PATIENT'S NAME: \_\_\_\_\_ DATE: \_\_\_\_\_

	NONE	MILD	MODERATE	SEVERE
THROBING	0) _____	1) _____	2) _____	3) _____
SHOOTING	0) _____	1) _____	2) _____	3) _____
STABBING	0) _____	1) _____	2) _____	3) _____
SHARP	0) _____	1) _____	2) _____	3) _____
CRAMPING	0) _____	1) _____	2) _____	3) _____
GNAWING	0) _____	1) _____	2) _____	3) _____
HOT/BURNING	0) _____	1) _____	2) _____	3) _____
ACHING	0) _____	1) _____	2) _____	3) _____
HEAVY	0) _____	1) _____	2) _____	3) _____
TENDER	0) _____	1) _____	2) _____	3) _____
SPLITTING	0) _____	1) _____	2) _____	3) _____
TIRING/EXHAUSTING	0) _____	1) _____	2) _____	3) _____
SICKENING	0) _____	1) _____	2) _____	3) _____
FEARFUL	0) _____	1) _____	2) _____	3) _____
PUNISHING/CRUEL	0) _____	1) _____	2) _____	3) _____

---

VAS                          NO PAIN    WORST POSSIBLE PAIN

\_\_\_\_\_

PPI

0 NO PAIN                          \_\_\_\_\_

1 MILD                                  \_\_\_\_\_

2 DISCOMFORTING                          \_\_\_\_\_

3 DISTRESSING                          \_\_\_\_\_

4 HORRIBLE                                  \_\_\_\_\_

5 EXCRUCIATING                          \_\_\_\_\_

[figure not shown]
© R. Melzack 1984

The short-form McGill Pain Questionnaire (SF-MPQ). Descriptors 1–11 represent the sensory dimension of pain experience and 12-15 represent the affective dimension. Each descriptor is ranked on an intensity scale of 0 = none, 1 = mild, 2 = moderate, 3 = severe. The Present Pain Intensity (PPI) of the standard long-form McGill Pain Questionnaire (LF-MPQ) and the visual analogue scale (VAS) are also included to provide overall intensity scores.

[figure not shown]
The McGill Pain Questionnaire: Major properties and scoring methods . Melzack, 1987

## APPENDIX 2. STUDY PARTICIPANT FLOWCHART

### APPENDIX 3. CONSORT FLOWCHART

*\*Based on CONSORT Flowchart (Moher et al, 2001)*
